Potential candidates will primarily be identified using the EMR, which contains information such as patient demographics, coded encounters, and clinic stop codes. Based on prior CIH work, a conservative estimate of a 30% response rate has been assumed for this study. Thus, up to 40 primary care patients who meet pre-screening criteria (see below) will be screened in order to achieve a target enrollment of up to 12 Veterans. Using previously effective recruitment methodology, candidates will be mailed introductory letters that describe the study, how to volunteer, and how to opt out. Veterans who do not opt out will be considered eligible for recruitment phone calls. A trained RA will conduct recruitment phone calls to verify Veterans' age and contact information; establish capability of communicating in English; provide additional information about the study; and conduct further screening for TBI and relevant psychiatric history. Eligible and interested Veterans will subsequently be offered times to attend an in-person or telehealth/telephone meeting to complete informed consent procedures and their screening/ baseline assessment. In the case of telehealth/telephone consent, copies of consent forms and relevant surveys/ study measures will be provided by mail; verbal consent will be gathered, and signed consent forms (including copies for participants' records) will be returned by mail. Follow-up phone contact will take place on an as-needed basis (e.g., to schedule/ re-schedule study visits, respond to participant questions, clarify the nature missing or ambiguous responses on study measures, deliver telehealth/telephone sessions). In the event that a participant is lost to follow-up, we will send a letter if attempts at phone contact are unsuccessful.

[figure not shown]

Figure 1. Study Flow Process.

Phase 1 Inclusion Criteria:

- a) OEF/OIF/OND Veteran; b) \geq age 18; c) enrolled in VA primary care (appointment within last 12 months); d) history of mTBI (as measured by the *Ohio State Traumatic Brain Injury Identification Method-Short Form*; OSU TBI-ID; Corrigan & Bogner, 2007); e) persistent post-concussion-like symptoms (as measured by the NSI; Cicerone & Kalmar, 1995); f) BSI-18 (Derogatis, 2001) GSI T-score > 53 ; g) English speaking, able to read and write, and able to comprehend study materials.

Phase 1 Exclusion Criteria:

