- a) Prior, current, or pending enrollment in a cognitive rehabilitation program or other specific TBI rehabilitation program; b) moderate to severe TBI or other major neurocognitive disorder; c) psychotic disorder (e.g., schizophrenia spectrum disorder, delusional disorder, schizotypal personality disorder, bipolar or depressive disorder with psychotic features); d) acute suicidal ideation; e) inpatient psychiatric hospitalization within the past 12 months; f) any other illness or condition that would preclude or predictably influence ability to appropriately engage in study visits, as determined by the study team; g) active receipt of other mental health services during enrollment or active intervention period, except for stable psychotropic medications (≥ 1 month with no dose or medication changes).

Given high documented rates of MH comorbidity among Veterans with history of mTBI, individuals with current depression or PTSD symptoms will be permitted to enroll, as long as symptoms are not so functionally-impairing that they would preclude study participation. Exclusion criteria **a-d** are similar to those reported in a previous trial of full-length PST (Bell et al., 2017). Criteria **e-f** were added to narrow the target sample to the most likely candidates for PC-MHI, as opposed to specialty MH treatment, programs. The purpose of criterion **g** is to improve the likelihood that observed treatment effects are due to participation in the

intervention as opposed to other mental health services. Relative to exclusion criterion **a**, participants who have previously completed a cognitive assessment for research or clinical purposes, or who have received general clinical feedback on cognitive performance will be permitted to enroll as these are considered routine care and not cognitive rehabilitation.

Phase 1 Measures and Materials.

Measures are described below and summarized in Table 1.

a) Study Pre-Screening: Will be conducted via EMR review to establish service era status, primary care enrollment, and age (inclusion criteria **a-c**), and chart data points that signal probable mTBI history (see below) or possible exclusion criteria.

b) Study Screening/ Baseline Assessment: Screening and baseline assessment will consist of the following measures that are estimated to require 15-30 minutes:

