- Demographic Survey: The demographic survey will collect basic information on participants such as age, racial and ethnic background, gender, vocational, and socioeconomic status. Additional questions will inventory any PST-related and/or compensatory skills that Veterans may independently endorse prior to beginning study interventions.
- *OSU TBI-ID* (Corrigan & Bogner, 2007): A brief, structured screen designed to determine lifetime history of TBI by identifying possible head/neck injuries and associated loss or alterations of consciousness. Scores of 2 or 3 indicate a likely history of mTBI and will be used to establish inclusion criterion **d**. The OSU TBI-ID is a NINDS CDE.
- *NSI* (Cicerone & Kalmar, 1995): A 22-item checklist of common affective, cognitive, and somatosensory symptoms commonly reported after concussion. Sample items pertain to dizziness, headaches, and forgetfulness. This measure is commonly used in VA's second-level TBI evaluations, and is a NINDS CDE. An embedded Validity-10 index (Vanderploeg et al., 2014) estimates the likelihood of symptom exaggeration. Scores of 2 (moderate) or higher on at least one cognitive, affective, and somatic symptom will indicate possible persistent post-concussion-like symptoms (inclusion criterion **e**).
- *BSI-18* (Derogatis, 2001): The BSI-18 is a brief measure of psychological distress brought about by common somatic and affective symptoms. It has been validated for use in patients with history of TBI (Meachen et al., 2008) and is appropriate for use in primary care (Lang, 2005). BSI-18 GSI T-scores will be used to gauge inclusion criterion **f**. A score > 0 on Item 17 will serve as a signal to conduct further suicide risk assessment per the protocol specified below.
- *PHQ-9* (Kroenke et al., 2001): A standard measure of depression symptoms validated for use in primary care. A score > 0 on Item 9 will serve as a signal to conduct further suicide risk assessment per the protocol specified below.
- *PCL-5* (Bovin et al., 2015): A standard measure of post-traumatic stress symptoms.
- *Coronavirus Anxiety Scale (CAS)* (Lee, 2020): A brief mental health screen for coronavirus-related anxiety.

c) Mid-Intervention Measures:

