- Behavioral Health Measure-20 (BHM-20; Kopta & Lowry, 2002): A brief measure of emotional distress and life functioning, normed for use in primary care (Bryan et al., 2014). It consists of 3 subscales that measure general well-being, MH symptoms, and life functioning. The 4-item life functioning subscale (which evaluates work/ school and relationship functioning, as well as general quality of life) will be administered during each session attended during the open trial for routine outcome monitoring.

- Qualitative Interview: A brief (~5-item) semi-structured interview designed to gather patient feedback on each individual treatment session. Participants will be asked to provide details on the acceptability of each treatment component and perceived value of the skills that were reviewed (Proctor et al., 2011). The interview is designed to be flexible to allow for follow-up to participant responses; a tentative schedule is included with this submission. We estimate that interviews will require 15 minutes, though additional time will be allotted in the event that Veterans wish to elaborate further on any aspect of the interview.

d) Post-Intervention Measures (see descriptions above): BSI-18 (primary clinical outcome); NSI, PHQ-9, PCL-5, CAS (secondary clinical outcomes).

Table 1. Phase 1 Measurement/ Assessment Schedule.

	Chart Pre-Screening	Baseline Assessment	Individual Sessions	Post-Intervention
EMR Review	•			
Demographic Survey		•		
OSU-TBI-ID		•		
NSI		•		•
BSI-18		•		•
PHQ-9		•		•
PCL-5		•		•
CAS		•		•
BHM-20 (Life Functioning Subscale)			•	
Qualitative Interview			•	
Feasibility Measures	Staff will monitor throughout the study			

e) Study Feasibility Measures:

- *Feasibility of recruitment* will include the following descriptive statistics: the relative proportion of Veterans excluded per pre-screening criteria vs. screen-eligible Veterans; the relative proportion of screen pass vs. screen failures; reasons for screen failures; the number of participants enrolled per week; total time to sample accrual; and the proportion of the intent-to-treat sample with clinically-significant depression, and/or PTSD.

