Screening/ Baseline Assessment & Selection. Veterans who provide consent will be formally screened using the measures outlined above. Veterans who meet criteria will be invited to stay in the study; those who do not will be informed of their disposition and thanked for their time.

Intervention. The E-PST intervention will be administered to all participants in this open trial by a trained, therapist (Master's level-equivalent or higher). E-PST will consist of up to 6, 30-minute sessions focused on: a) reducing psychological distress by enhancing specific problem-solving skills; and b) developing specific cognitive and behavioral skills that target common cognitive inefficiencies reported in Veterans with mTBI history. The current therapist guide and participant workbook are included with this submission. We anticipate that sessions will be scheduled biweekly, but will afford flexibility in scheduling to aid in our assessment of feasibility of this planned approach. Psychological distress data (BHM-20 life-functioning subscale) will be collected during treatment sessions as part of routine outcome monitoring. Sessions will be audio-recorded for training and supervision purposes.

Qualitative Interview. Following completion of each E-PST session, study staff will conduct a brief semi-structured interview with participants to gather data on their opinions of the intervention. Interviews will be conducted in-person following treatment sessions or else later by phone. A trained RA will take notes on participant comments via a flip chart/ spreadsheet to facilitate rapid qualitative analysis (see below). Interviews will be recorded to serve as part of the audit trail. Flip chart data will be reviewed by the RA, under the PI's supervision, and cross-referenced with audio to ensure accuracy prior to analysis.

Post-Intervention Assessment. Clinical outcome measures (BSI-18, NSI, PHQ-9, PCL-5) will be administered following the final treatment session. Veterans who discontinue early will be invited to complete clinical outcomes at a time (e.g., 12-week mark) when they otherwise would have completed the final session.

Participant Payment. Participants will be provided a maximum \$75 stipend at the conclusion of the study according to the following schedule: \$10 for completion of each post-session study interview (up to 6 visits) and a \$15 stipend at screening/ baseline assessment.

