Risk Management. RA's will monitor for signals of clinical need at study assessment time points (e.g., participant statements of concern, ratings of suicidal ideation), and study therapist(s) will monitor such signals at intervention visits. New or worsening ratings that pertain to suicidal ideation will be addressed using the procedure outlined below. Adverse events will be monitored and reported according to institutional protocols.

Phase 1 Quantitative Data Analysis

Feasibility: As this trial will provide us with feasibility information in preparing for our pilot RCT, we will describe the number of participants screened and enrolled per month, proportion of screened participants who are eligible to enroll, completion rates of treatment sessions, patient attrition rate and other relevant variables. Recruitment will be displayed by plotting the cumulative number of patients enrolled into this study and compared to the anticipated rate of recruitment. Graphs will also be utilized to display rates of intervention and assessment retention at each measurement time. Descriptive statistics will be calculated for each of the feasibility and fidelity indicators described above (e.g., measurement, treatment fidelity). Study therapist fidelity will be described quantitatively with the mean number of items endorsed in fidelity checklists. Items with relatively low fidelity will inform revisions to the training curriculum that will be designed for E-PST therapists in our pilot RCT.

Clinical outcomes: Given the small sample, we are precluded from conducting an advanced quantitative analysis of these data. We will however use an appropriate level of descriptive analysis to explore the clinical effect of E-PST. Descriptive statistics will be calculated and reviewed for relevant participant demographic variables. Individual line graphs of pre-post BSI scores will be generated, and mean differences in BSI-18 scores will be compared. We will also calculate the percentage of participants who report a clinically-significant change on the BSI-18 will be calculated. Additionally, BHM-20 data will be reviewed for each participant after each session. Trends of changes in scores will be visually inspected over time to evaluate evidence of a preliminary clinical effect.

Phase 1 Qualitative Data Analysis

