Acceptability: Veteran feedback on acceptability of E-PST will primarily be analyzed via rapid qualitative analysis (Beebe, 2001) of interview data. This approach will facilitate our ability to quickly incorporate patient feedback in making final revisions to the treatment manual that will be used in our future RCT. If our analyses reveal consistent concerns related to E-PST, we will make any necessary adjustments prior to finalizing the manual that will be used in the subsequent RCT. For example, if $\geq 20\%$ of Veterans describe difficulty interpreting content of a treatment module, we will conclude that there is sufficient consistency across participants to suggest the need for modification in that domain in our future trial. The team will meet to evaluate the feasibility and appropriateness of a change in content, and consider options such as adjusting language to reflect a more lay approach to terminology, re-organizing session content to improve session flow and interpretability, or removing potentially confusing content. If larger changes are required as a result of Veteran feedback, we will seek follow-up consultation and feedback from subject matter experts before changes to the protocol are finalized.

Phase 1 Sample Size Justification

Our primary goal for this study is to gather preliminary feedback from Veteran stakeholders in order to establish evidence that the proposed intervention is both feasible and acceptable, with a secondary goal of evaluating the potential clinical effect of E-PST. Previous work has shown that our target sample of up to 12 participants will be adequate to glean sufficient breadth of stakeholder opinions (Guest et al., 2006; Palinkas et al., 2015). A more comprehensive evaluation of feasibility and treatment satisfaction will later be conducted as part of the RCT. As the small sample size precludes robust statistical analyses, we will focus our quantitative observations solely on descriptive data.

Phase 1 Data Attrition

As this is an adapted intervention, we do not presently have robust estimates of the level of sample and data attrition expected for this open trial. However, our intended sample (up to $n = 12$ Veterans) is intentionally small. We are prepared to sample with replacement should we need to enroll more than 12 Veterans to achieve the minimum sample of treatment participants necessary to reach qualitative data saturation, and will amend the study as necessary if additional participants are needed.

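### Phase 1 reads pre-post BSI-18 change as a preliminary clinical effect, although the 'pre' score is the one that selected the Veterans and there is no control arm

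*Combined protocol and SAP*

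**What the plan says.** All references are to the combined protocol and SAP.

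- **Entry.** Phase 1 Inclusion Criteria, item f, requires "BSI-18 (Derogatis, 2001) GSI T-score > 53". Phase 1 Measures and Materials, section b, confirms the source: "BSI-18 GSI T-scores will be used to gauge inclusion criterion" f.
- **One pre-treatment score.** Screening and baseline are a single assessment: "Screening and baseline assessment will consist of the following measures that are estimated to require 15-30 minutes". Under Phase 1 Procedures, "Veterans who provide consent will be formally screened using the measures outlined above". Table 1 places the BSI-18 at Baseline Assessment and Post-Intervention only.
- **Outcome.** Section d of the measures lists "BSI-18 (primary clinical outcome); NSI, PHQ-9, PCL-5, CAS (secondary clinical outcomes").
- **Analysis.** Phase 1 Quantitative Data Analysis, Clinical outcomes: "Individual line graphs of pre-post BSI scores will be generated, and mean differences in BSI-18 scores will be compared". The percentage of participants with clinically significant change is also planned, but no BSI-18 threshold for it is given. The stated purpose is to explore what E-PST does clinically.
- **Aim.** The Phase 1 Sample Size Justification puts feedback on feasibility and acceptability first, "with a secondary goal of evaluating the potential clinical effect of E-PST".
- **No comparison group.** Every Phase 1 participant receives E-PST and continues usual primary care. The text mentions no second baseline, no adjustment and no caveat about regression to the mean.

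**The concern.** A score that had to exceed a cut to be counted contains, on average, some upward error or a temporary peak. When the same people are measured again, the average moves back toward the population mean without any treatment. Here the selected score is the starting point of every planned BSI-18 summary, and no control arm is available to subtract the drift. Natural recovery and continued usual care could add to it.

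At stake is what Phase 1 may say on its secondary goal. An inert intervention would be expected to show a mean improvement on the named primary clinical outcome and a somewhat inflated share of improvers. The NSI has the same feature: it defines entry criterion e and is a secondary post-intervention outcome.

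**Working it through.** **The plan's own figure.** The documents state no expected Phase 1 BSI-18 change, power or effect size. The one Phase 1 planning figure reproduces: 40 screened × 0.30 response = 12 enrolled.

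**Inputs.**
- Cut: GSI T > 53, from the inclusion criteria. On whole T-scores this means 54 or more, so c = 53.5.
- SD of the T-score in the screened population: not given; assumed 10.
- Mean μ of the screened population: not given; assumed 50 to 65.
- Correlation r between the screening and post-treatment scores: not given; assumed 0.6 to 0.9.

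**Formula.** With bivariate normal scores and no treatment effect,

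expected fall = (1 − r) × SD × λ(a), where a = (c − μ)/SD and λ(a) = φ(a)/(1 − Φ(a)).

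**Worked case.** For μ = 50, a = (53.5 − 50)/10 = 0.35 and λ = 1.033. At r = 0.7 the fall is 0.3 × 10 × 1.033 = 3.1 T points.

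**Expected fall in T points with no treatment effect:**

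| Screened mean | r = 0.6 | r = 0.7 | r = 0.8 | r = 0.9 |
|---|---|---|---|---|
| 50 | 4.1 | 3.1 | 2.1 | 1.0 |
| 55 | 2.8 | 2.1 | 1.4 | 0.7 |
| 60 | 1.7 | 1.3 | 0.9 | 0.4 |
| 65 | 0.9 | 0.7 | 0.5 | 0.2 |

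Simulation with rounded T-scores (2 million pairs per cell) agrees with these values. Relative to the SD of the selected baseline scores, the spurious standardized change is 0.03 to 0.76.

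**What 12 Veterans would show with no effect.** Across the same cells, the group mean falls at all in 56% to 96% of samples, against 50% without selection. It falls by 2 points or more in 9% to 82%.

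**Share of improvers.** If clinically significant change is taken as a fall of 5 T points (an assumption), 17% to 48% would qualify with no effect. In an unselected group with the same correlations the figure is 16% to 31%. Selection inflates the share, but much of it is ordinary retest variation.

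**Would a repeat baseline remove it?** Let r12 be the correlation of the screening score with a session 1 score, and r13 its correlation with the post score. The expected untreated fall from session 1 to post is

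(r12 − r13) × SD × λ(a).

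- If r12 = r13 this is zero. Simulation under equal correlations gave −0.01 to 0.01 in all eight scenarios run.
- If session 1 follows screening closely, r12 may be higher. With r12 = 0.9 and r13 = 0.7 the residual is 0.2 × 10 × λ = 2.1, 1.4 or 0.9 points for means of 50, 55 or 60. The corresponding falls from the screening score are 3.1, 2.1 and 1.3, so about two-thirds remains.

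The documents do not state the interval between screening and session 1.

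**The case against.** The strongest reply is that nothing depends on this number and the plan already limits its claims. Most of that stands.

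- **Progression.** A reader might infer that a spurious improvement could carry E-PST into Phase 2. The documents do not support this. The opening section ties advancement to feasibility and acceptability, the Phase 1 Study Timeline moves to the pilot RCT without a BSI-18 condition, and the one numeric action rule (20%) concerns difficulty interpreting module content.
- **Phase 2.** A reader might infer that its effect size or sample size inherits the problem. It does not. Phase 2 randomizes 1:1, so regression to the mean is expected to be equal in both arms, and its sample size rests on published effect data and a confidence-interval method.
- **Size.** It is tempting to set a 3-point fall beside the 0.3 SD used in the Phase 2 sample size. That figure is a between-arm standardized difference, not a pre-post change. The fall may also be small: criterion e already requires symptoms in three domains, and Phase 2 makes T ≥ 63 one of two randomization strata, so screened means well above the cut are plausible.
- **Modest language.** The plan calls its Phase 1 quantitative observations descriptive and the effect preliminary. It also reviews BHM-20 life functioning scores by session, a measure not used for selection. This is partial mitigation only: the subscale has four items, is not the primary clinical outcome, and has no control either.

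What the reply does not remove is the bias. A descriptive mean change is still shifted when its baseline was selected, and the text offers that change as bearing on clinical effect without saying so.

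**Conclusion.** The point holds, as a minor-to-moderate issue confined to the secondary goal of Phase 1. The structure is in the text: the same score selects and serves as 'pre', there is no control, and the change is read as a preliminary clinical effect. For any retest correlation below 1 the expected untreated change is a fall, so the direction is certain in expectation.

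The size is not certain. It is about 0.2 to 4.1 T points under assumed values (SD 10, mean 50 to 65, correlation 0.6 to 0.9, normal scores), and the documents cannot show which end applies. Nor should a reader infer that Phase 1 is bound to show an improvement: with 12 Veterans and no effect, the mean may fail to fall.

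**What to change.** **Main change, at no cost in data collection.** In Phase 1 Quantitative Data Analysis (Clinical outcomes) and the Phase 1 Sample Size Justification:

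- Describe the BSI-18 result as uncontrolled pre-post change that includes regression to the mean from the entry cut.
- Report beside it the change expected under no effect, over a stated range of mean, SD and correlation such as the table above.
- Do not describe the result as evidence of a clinical effect of E-PST.
- Apply the same wording to the NSI.
- State in advance the BSI-18 threshold for clinically significant change.

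This wording can still be adopted if Phase 1 data have already been collected.

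**Optional addition.** Repeat the BSI-18 before any session 1 content, where BHM-20 items are already collected, and use that score as 'pre'. A reader might call such a score unselected, but it comes from Veterans chosen on a correlated score. It reduces the artefact and removes it fully only if r12 = r13. Natural recovery and usual care remain either way, so the wording change is still needed.

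The cost of the addition is one 18-item form for up to 12 Veterans, a few minutes of a 30-minute session, an additional Item 17 response to be handled under the existing risk procedure, and probably a smaller reported change.

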Demographic Survey		•			
Ohio State Traumatic Brain Injury Identification Method-Short Form (OSU TBI-ID)		•			
Neurobehavioral Symptom Inventory (NSI)		•		•	•
Brief Symptom Inventory-18 (BSI-18)		•		•	•
Patient Health Questionnaire-9 (PHQ-9)		•		•	•
PTSD Checklist for DSM-5 (PCL5)		•		•	•
Coronavirus Anxiety Scale (CAS)		•		•	•
Applied Cognition-General Concerns-Short Form (ACGC-8a)		•		•	•
Applied Cognition-Abilities-Short Form (ACA-8a)		•		•	•
Hopkins Verbal Learning Test-Revised (HVLT-R)		•		•	•
Trail Making Test Parts A and B (TMT-A, TMT-B)		•		•	•
Wechsler Adult Intelligence Scale- Fourth Edition (WAIS-IV) Digit Span		•		•	•
Alcohol Use Disorders Identification Test (AUDIT)		•		•	•
Brief Addictions Monitor-Revised (BAM-R)		•		•	•
Pain Symptom Survey (PEG)		•		•	•
World Health Organization Quality of Life - BREF (WHOQOL-BREF)		•		•	•
General Self-Efficacy Scale (GSES)		•		•	•
Patient Global Impressions of Change (PGIC)				•	•
Client Satisfaction Questionnaire (CSQ)				•	•
Qualitative Interview				•	
Behavioral Health Measure-20 (BHM-20) Life Functioning Subscale			•		
Feasibility Metrics		•	•	•	•

Intervention. The test (E-PST) or control intervention will be administered to participants by a trained, therapist (Master's level-equivalent or higher). Psychological distress data (BHM-20 life-functioning subscale) will be collected during treatment sessions as part of routine outcome monitoring. Sessions will be audio-recorded for training and supervision purposes.

- **Test intervention (E-PST).** E-PST consists of 6, approximately 30-minute sessions focused on: a) reducing psychological distress by enhancing specific problem-solving skills; and b) developing specific cognitive and behavioral skills that target common cognitive inefficiencies reported in Veterans with mTBI history. The current therapist guide and participant workbook are included with this submission. We anticipate that sessions will be scheduled approximately biweekly but will afford flexibility in scheduling to aid in our assessment of feasibility of this planned approach.

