Primary analyses will focus on detecting post-treatment change in psychological distress as measured by the BSI-18's GSI T-score. We will test the preliminary hypothesis that E-PST (vs. control) will be associated with reduced psychological distress as measured by BSI-18. BSI-18 data will be described with means, standard deviations and CIs at each time point and condition. To show central tendency, variation and potential trends over time, means and 95% CIs will be plotted across time for each condition. Additional line plots connecting means across time will overlay the CIs to help illustrate trends. To assist in developing a larger trial, an ES will be calculated at post treatment to describe the standardized difference between conditions. The ES will be calculated by dividing the difference in the mean BSI-18 score between conditions at post-treatment by the pooled standard deviation. Then, the upper limit of a one-sided 80% CI under the null hypothesis of no difference between groups (ES = 0) will be compared to the observed ES by using the non-central *t*-distribution method discussed by Cumming & Finch (2001). We opted for a one-sided CI because we are interested in progressing toward a larger trial based on some evidence of effectiveness. The lower end of the CI is not informative in this pilot as the progression towards a larger trial would not occur even if the control condition was marginally more effective than E-PST. While a standard 95% CI provides greater coverage of the population difference, it also requires a larger sample of patients and associated increases in cost and time. Therefore, we propose an 80% interval that provides reasonable assurance of making the correct decision to move on to a larger trial (Cocks & Torgerson, 2013) While primary analyses focus on psychological distress, post-treatment ES's will also be calculated for secondary outcomes, and a correlation matrix will be built to describe the degree of correspondence among all outcomes. Our goal is to calculate a preliminary ES estimate that is representative of the true population using the ITT principle. Thus, all patients who are complete a baseline assessment and are randomized will be included in our analysis. We plan to utilize two sophisticated methods with the first being Maximum Likelihood Estimation (MLE), and Multiple Imputation (MI) as the second. A multi-level model (MLM) will be developed using MLE to calculate means and standard errors that will be used in the formation of an ES. MLM provides unbiased parameter estimates under a missing at random (MAR) assumption without resorting to listwise deletion of patients due to missing data. While the validity of MAR cannot be fully determined from the data, the reason for the missingness may depend on observed co-variates. If the latter case is true, MI (see below) is a viable and powerful option for imputing

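### Phase 1 reads the BHM-20 life-functioning trend as evidence of a clinical effect, but the scale is scheduled only at attended sessions, with no baseline or post-intervention score (minor)

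*Combined protocol and SAP*

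**What the plan says.** Phase 1 Measures and Materials, under Mid-Intervention Measures, states that the BHM-20 life-functioning subscale "will be administered during each session attended during the open trial for routine outcome monitoring". The Intervention paragraph of Phase 1 Procedures agrees: "Psychological distress data (BHM-20 life-functioning subscale) will be collected during treatment sessions as part of routine outcome monitoring". Table 1 has one mark for the scale, in the Individual Sessions column.

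The scale is in none of the Phase 1 assessments made outside the sessions. The baseline section opens with "Screening and baseline assessment will consist of the following measures that are estimated to require 15-30 minutes", and the list that follows does not include it. The post-intervention list is "BSI-18 (primary clinical outcome); NSI, PHQ-9, PCL-5, CAS (secondary clinical outcomes"; the list in the Post-Intervention Assessment paragraph of Procedures does not include it either. That paragraph invites Veterans who discontinue early to complete the clinical outcomes when their final session would have fallen, with 12 weeks as the example.

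Phase 1 Quantitative Data Analysis, Clinical outcomes, plans pre-post line graphs and mean differences for the BSI-18. It then adds that BHM-20 data will be reviewed participant by participant after each session, and continues: "Trends of changes in scores will be visually inspected over time to evaluate evidence of a preliminary clinical effect". Phase 1 Sample Size Justification names the potential clinical effect of E-PST as a secondary goal.

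**The concern.** The measures and procedures sections describe the subscale as session monitoring. The analysis section asks it to show whether treatment had an effect. Collection at attended sessions suits the first use. The second needs a score from before treatment and one from after it, obtained whether or not the Veteran stayed.

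Without those, a rising line shows only what happened between the first and last attended sessions. There is no control arm in this open trial to set it against. The Veterans whose later course is unknown are those who stopped, and the plan expects incomplete attendance: under the Phase 1 Approach, attending fewer than six sessions is not a protocol deviation. At stake is how one of the two clinical measures named in the Phase 1 outcome analysis (BSI-18 and BHM-20) will be read and reported.

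**Working it through.** No power, sample-size or error-rate figure bears on this point, and the plan gives no figure to reproduce. The check compares the two measures and then counts scores.

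**Schedule, side by side (Phase 1)**

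| | BSI-18 | BHM-20 life functioning |
|---|---|---|
| Baseline assessment | yes | no |
| Treatment sessions | no | yes, if attended |
| Post-intervention | yes | no |
| Sought from early discontinuers | yes | no |
| Analysis | pre-post graphs, mean difference, percentage with clinically significant change | visual trend, as evidence of effect |

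**Scores per Veteran**

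Inputs: at most 6 sessions, scheduled biweekly with flexibility (Phase 1 Procedures, Intervention). I take biweekly as every two weeks, which is consistent with six sessions and the 12-week example given for early discontinuers.

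A Veteran who attends the first k sessions and then stops has k scores. For k of 1 or more, they span 2 × (k − 1) weeks from session 1. A full series spans 2 × (6 − 1) = 10 weeks, so the stretch not seen before the session-6 date is 10 − 2 × (k − 1) weeks.

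| Sessions attended (k) | Scores | Weeks covered | Weeks not seen before session-6 date |
|---|---|---|---|
| 0 | 0 | none | all |
| 1 | 1 | 0 (no change can be formed) | 10 |
| 2 | 2 | 2 | 8 |
| 3 | 3 | 4 | 6 |
| 4 | 4 | 6 | 4 |
| 5 | 5 | 8 | 2 |
| 6 | 6 | 10 | 0 |

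A completer also has no score after session 6. The text does not say whether the subscale is given before or after the content of a session, and it does not name the session-1 score as a baseline, so the start of every series is undefined.

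**How often series will be short**

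This cannot be taken from the plan. Phase 1 Data Attrition says there is no robust estimate for the open trial. That section provides for enrolling further Veterans, but neither it nor the analysis section says how a shortened BHM-20 series is to be read.

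**The case against.** The case on the other side is strong on weight. The BHM-20 is not a designated Phase 1 outcome: the primary is the BSI-18, and the secondaries are the NSI, PHQ-9, PCL-5 and CAS. The analysis section brings the BHM-20 in as an addition. Feasibility and acceptability come first, the analysis is descriptive, and Phase 1 Study Timeline moves to the pilot RCT with no BHM-20 criterion. Sessions attended and reasons for dropout are reported among the retention measures, and early discontinuers are still asked for the BSI-18. A session-1 score taken before any content could serve as a near-baseline.

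All of that stands and makes the point minor. It does not remove the sentence that reads the trend as evidence of effect, and the plan does not define the session-1 score as the start.

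A reader might infer more than the documents support:

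- *That Phase 2 lacks an effect size it promises.* Table 2 marks "Behavioral Health Measure-20 (BHM-20) Life Functioning Subscale" only at mid-intervention, and the Phase 2 analysis says "post-treatment ES's will also be calculated for secondary outcomes". But no section names the BHM-20 as a Phase 2 secondary outcome or plans a between-arm analysis of it. The WHOQOL-BREF covers quality of life and disability at T1, T2 and T3.
- *That attendance will differ by arm and bias a Phase 2 comparison.* Nothing in the documents establishes such a difference, and no such comparison is planned.
- *That the group trend will suffer survivor bias.* Review is by participant. The bias would arise only if series were pooled across sessions, which is not stated.
- *That a Veteran who gets worse and leaves shows no decline.* Worsening across attended sessions is recorded; only what follows the last one is missed.
- *That the loss can be sized from Phase 2 Data Attrition.* That section gives about 6% participant attrition over 12 weeks and 20% over 6 months in other trials. Neither is a rate of session dropout in Phase 1.

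**Conclusion.** The concern holds for Phase 1 only, and it is minor. A scale scheduled solely at attended sessions is to be inspected for evidence of a clinical effect, although its series have no defined pre-treatment start and end at the last attended session. For a Veteran with one session there is no change to inspect. For one who leaves after session 3, the series covers 4 of the 10 weeks a completer would give, on the two-week reading of biweekly. The number of Veterans affected is unknown.

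The primary clinical outcome is not affected, the sample is at most 12, and no estimate, test or progression rule depends on the trend. The conclusion assumes that the sentence on trends refers to the BHM-20 data named immediately before it, which is its natural reading.

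**What to change.** Add the four life-functioning items to the Phase 1 baseline and post-intervention assessments, including the assessment already offered to Veterans who discontinue early. Mark both in Table 1. In Clinical outcomes, rest any BHM-20 statement of effect on the baseline to post-intervention contrast, and describe the session scores as on-treatment monitoring.

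If Phase 1 data are already collected, name the session-1 score as the start point, show each series by number of sessions attended, and do not present the trend as evidence of effect. That route needs only a change of wording and presentation.

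The cost of the full change is four more items at two assessments that already take place, a small added burden for participants. No change to Phase 2 is needed on this point.
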